6.2. Exclusion Criteria

Patients will be excluded from study enrollment if they meet any of the following criteria at screening:

- [6] Are currently enrolled in any other clinical trial involving an investigational product or any other type of medical research judged not to be scientifically or medically compatible with this study
- [7] Have received any prior, or are currently receiving, treatment with any bDMARD therapy or small-molecule for PsA or for psoriasis, including investigational therapies (such as but not limited to TNF inhibitors, IL-1 receptor antagonists, IL-6 inhibitors, anti-IL-12/23p40 therapies, T cell or B cell targeted therapies, or Janus kinase inhibitors).
 - Exception: previous treatment of phosphodiesterase type 4 inhibitors will be permitted. Treatment with phosphodiesterase type 4 inhibitors must have been discontinued at least 8 weeks before randomization (Visit 2).
- [8] Have previously completed or withdrawn from this study or any other study investigating ixekizumab or other IL-17 inhibitors, eg, anti-IL-17 or anti-IL-17 receptor (anti-IL-17R) monoclonal antibodies.
- [9] Have a history of drug-induced Ps.
- [10] Have used csDMARDs other than MTX, leflunomide, sulfasalazine, or cyclosporine in the 8 weeks prior to randomization (Visit 2).
 - Have discontinued MTX, sulfasalazine, or cyclosporine within 12 weeks prior to randomization.

If taking MTX, leflunomide, sulfasalazine, or cyclosporine, must have been treated for at least 12 weeks prior to randomization *and* on a stable dose for at least 8 weeks prior to randomization, as follows: oral or parenteral MTX = 10 to 25 mg/week, leflunomide = 20 mg/day, sulfasalazine = up to 3 g/day, or cyclosporine up to 5 mg/kg/day. The dose of these allowed concomitant medications must remain unchanged during the first 24 weeks of the Open-Label Treatment Period unless changes are required for safety issues. Local standard of care should be followed for concomitant administration of folic acid with MTX.

- [11] Have discontinued leflunomide within 4 weeks prior to randomization or have received leflunomide from 4 to 12 weeks prior to randomization and have not undergone a drug elimination procedure.
- [12] Use of oral corticosteroids at average daily doses of >10 mg/day of prednisone or its equivalent, or use of variable doses of any oral corticosteroids, within 4 weeks prior to randomization (Visit 2).

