7.7. Concomitant Therapy

All concomitant medication taken during the study must be recorded on the Concomitant Medication case report form (eCRF) at the study visits indicated in the Schedule of Activities (Section 2). Treatment with concomitant PsA therapies during the study will be permitted only as outlined in the inclusion and exclusion criteria (Sections 6.1 and 6.2, respectively) and as described below. Patients taking permitted PsA medications should be on stable doses at randomization (Visit 2) and through the first 24 weeks of the Open-Label Treatment Period, as specified below, unless changes are required for safety reasons. Table RHCF.7.2, Table RHCF.7.3, and Table RHCF.7.4 summarize concomitant medications that are and are not permitted and the conditions for use during the study for those which are permitted.

Table RHCF.7.2. Concomitant Medications Permitted/Not Permitted in the Open-Label Treatment Period from Week 0 to Week 24 for Treatment of PsA and Chronic Conditions

Drug Class	As Needed	Chronic Use	Conditions for Use
bDMARDs	N	N	Not allowed
PDE4 or JAK inhibitors	N	N	Not allowed
csDMARDs	N	Y	Stable dose allowed. Stable doses with no dose adjustments, changes, and/or introduction of a new csDMARD Allowed doses: Oral or parenteral MTX; 10 to 25 mg/week Leflunomide: up to 20 mg/day Sulfasalazine: up to 3 g/day Cyclosporine: up to 5 mg/kg/day
Live vaccines (including BCG)	N	N	Not allowed
Phototherapy	N	N	Not allowed

Drug Class	As Needed	Chronic Use	Conditions for Use
NSAIDs, COX-2			Stable doses with no dose adjustments, changes,
inhibitors			and/or introduction of a new NSAID.
	N	Y	Allowed up to the maximum recommended doses
	11	1	for pain.
			Aspirin (doses not exceeding 350 mg/day) may
			be taken to manage cardiovascular risk.
Opiate analgesics			Stable doses with no dose adjustments, changes,
	N	Y	and/or introduction of a new opiate analgesic.
	1	_	May be used at average daily doses ≤30 mg/day
			of morphine or its equivalent
Nonopiod analgesics			Allowed up to the maximum recommended doses
(paracetamol and			for pain.
acetaminophen)			May be administered as needed basis during the
	Y	Y	study, but should be withheld within 24 hours of
			a visit.
			May be used at doses ≤1000 mg for
			premedication for allergic/hypersensitivity
			reactions from injections (see Section 7.8.3)
Topical steroids			Weak potency (WHO Group 1 classification
	Y	Y	only as needed, but not within 24 hours of PASI
			assessment

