[1b] Are women of non-childbearing potential, defined as either women who have had surgical sterilization or who are ≥60 years of age	Monitor	Monitor’s list: women who have had surgical sterilization.
[2] No confirmed diagnosis of PSA of at least 6 months prior to baseline or did not meet CASPAR criteria	Monitor	Monitor’s list
[3] <3 TJC or <3 SJC at Visit 1 or 2	Monitor	Monitor’s list.
[4] BSA <3% at Visit 1 or 2	Monitor and Stats	Monitor’s list. Check if BSA <3% either at Visit 1 or at Visit 2
[50] Have not been treated with 1 or more csDMARDs	Monitor and Stats	Monitor’s list and stats programming. Check past or present use for MTX, sulfasalazine, leflunomide, or hydroxychloroquine

Important Protocol Violation Category/Subcategory	Source to Identify Protocol Violation	Statistical Programming Guidance for Clinical Study Report
[6] Currently enrolled in any other clinical trial involving an investigational product or any other type of medical research judged not to be scientifically or medically compatible with this study	Monitor	Monitor’s list.
[7] Have received prior or currently receiving treatment with any biologic or small molecule therapy for PsA or Ps, including investigation therapies (such as, but not limited to, a TNF inhibitor, IL-1 receptor antagonists, IL-6 inhibitor; anti-IL-12/23p40, T cell or B cell targeted therapies, or Janus kinase inhibitors). Note: previous treatment of phosphodiesterase type 4 inhibitors will be permitted. Treatment with phosphodiesterase type 4 inhibitors must have been discontinued at least 8 weeks before randomization (Visit 2).	Monitor	Monitor’s list
[8] Previous or current medication exposure at Visit 1 to LY2439821 or IL-17 antagonists or previous participation in the current study. (Note: See protocol for patients who may be allowed to re-screen.)	Monitor	Monitor’s list
[9] Have history of drug-induced Ps.	Monitor	Monitor’s list
[10] Use of csDMARDs (other than MTX, leflunomide, sulfasalazine, or cyclosporine) within 8 weeks prior to Visit 2; or have discontinued MTX, leflunomide, sulfasalazine, or cyclosporine within 12 weeks prior to Visit 2.	Monitor	Monitor’s list
[11] Have discontinued leflunomide within 4 weeks prior to Visit 2 or from 4 to 12 weeks prior without drug elimination procedure.	Monitor and Stats	Monitor’s list, or, If the difference between Visit 2 date and medication end date <28 days for previous therapy, Leflunomide

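### Two wording errors in the leflunomide rules: protocol exclusion [11] as written bars continuing users whom [10] admits, and SAP Table RHCF.6.9 [10] calls a permitted stop a violation

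*Protocol*

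**What the plan says.** Protocol Section 6.2 opens with a rule that any single criterion is sufficient: "Patients will be excluded from study enrollment if they meet any of the following criteria at screening". Four provisions then bear on leflunomide.

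- **Protocol [10], continuing users.** "If taking MTX, leflunomide, sulfasalazine, or cyclosporine, must have been treated for at least 12 weeks prior to randomization", and the dose must have been stable for at least 8 weeks. Leflunomide is one of the named drugs.
- **Protocol [10], recent stoppers.** The 12-week rule reads "Have discontinued MTX, sulfasalazine, or cyclosporine within 12 weeks prior to randomization". Leflunomide is not in this list.
- **Protocol [11].** The first limb excludes a leflunomide stop within 4 weeks of randomization. The second limb excludes those who "have received leflunomide from 4 to 12 weeks prior to randomization and have not undergone a drug elimination procedure".
- **Protocol Section 7.7, Table RHCF.7.2.** csDMARDs, including leflunomide up to 20 mg/day, may continue from Week 0 to Week 24 under the condition "Stable doses with no dose adjustments, changes, and/or introduction of a new csDMARD".

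SAP Section 6.17, Table RHCF.6.9, restates the criteria as important protocol violations. Item [10] includes patients who "have discontinued MTX, leflunomide, sulfasalazine, or cyclosporine within 12 weeks prior to Visit 2", so leflunomide has been added. Its only source is the monitor's list. Item [11] reads "Have discontinued leflunomide within 4 weeks prior to Visit 2 or from 4 to 12 weeks prior without drug elimination procedure". Its source is both the monitor's list and a programmed check, and the programmed part is "If the difference between Visit 2 date and medication end date <28 days for previous therapy, Leflunomide".

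**The concern.** The two limbs of protocol [11] use different verbs: *discontinued* in the first and *received* in the second. A careful reader may take the difference as deliberate. On that reading the second limb reaches people who never stopped the drug, and it removes essentially every continuing leflunomide user whom [10] and Table RHCF.7.2 provide for. The opening of protocol Section 6 forbids waivers of enrollment criteria, so an eligibility rule should not depend on sites correcting it by inference. A site following the words could turn away or query an intended patient.

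The SAP error runs the other way. A patient who stopped leflunomide between 4 and 12 weeks before randomization and completed an elimination procedure is eligible, but fits the text of SAP item [10] as an important violation. The SAP also contradicts itself: if item [10] were right, the elimination condition in item [11] would have no function, because every stop within 12 weeks would already be a violation. A patient misflagged this way would enter the violation summary. That patient could also be dropped from the additional analyses of primary and/or major secondary endpoints in patients without some or all violations (SAP Section 6.17).

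**Working it through.** The plan states no figure here to reproduce. The check treats each rule as a logical condition and applies it to the possible leflunomide histories.

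**Inputs.** Protocol Section 6.2 [10] and [11]; SAP Table RHCF.6.9 [10] and [11], including the programming note. 4 weeks = 28 days and 12 weeks = 84 days. A continuing user is taken to have had at least 12 weeks of treatment on a stable dose and no elimination procedure. The elimination condition is applied to the second limb of [11] only.

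**Conditions.**
- Protocol [11] as written: excluded if stopped < 4 weeks before, or if any drug was received in the 4-to-12-week window and there was no elimination.
- Protocol [11] with *discontinued*: excluded if stopped < 4 weeks before, or if stopped at 4 to 12 weeks and there was no elimination.
- SAP [10] text: flagged if stopped < 12 weeks before, whether or not elimination was done.
- SAP [11] text: same condition as protocol [11] with *discontinued*.
- SAP [11] programmed check: flagged if stopped < 28 days before.

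| Leflunomide history | Protocol [11] as written | Protocol [11] with *discontinued* | SAP [10] text | SAP [11] text | SAP [11] programmed |
|---|---|---|---|---|---|
| Still taking, no elimination | **Excluded** | Not excluded | No flag | No flag | No flag |
| Stopped 2 weeks before, with or without elimination | Excluded | Excluded | Flag | Flag | Flag |
| Stopped 8 weeks before, no elimination | Excluded | Excluded | Flag | Flag | No flag |
| Stopped 8 weeks before, elimination done | Not excluded | Not excluded | **Flag** | No flag | No flag |
| Stopped 14 weeks before, no elimination | Not excluded | Not excluded | No flag | No flag | No flag |

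The two bold cells are the errors. In the first row, the protocol text excludes a patient whom [10] admits. In the fourth, SAP [10] flags a patient whom the protocol accepts and SAP [11] leaves alone.

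**Width of the SAP conflict.** 84 − 28 = 56 days of possible stop dates, and only when elimination was done.

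**After correction.** With *discontinued* in protocol [11] and leflunomide removed from SAP [10], the SAP [11] text and protocol [11] agree for every stop day from 0 to 199, with and without elimination (0 disagreements). No true violation is lost:
- Stops under 4 weeks, and stops at 4 to 12 weeks without elimination, remain covered by SAP [11].
- Current users treated for less than 12 weeks remain excluded by protocol [10].

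The third row shows that the programmed check misses stops at 4 to 12 weeks without elimination. These rest on the monitor's list. The table's footnote says a deviation with both sources appears if either one identifies it, so this is a dependence to know about and not a gap in the rule.

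**The case against.** The best defence of protocol [11] is context. The criterion opens with stopping leflunomide, an elimination procedure makes sense only for someone who has stopped, and [10], immediately above, deals expressly with those still taking it. Table RHCF.7.2 and SAP [11] point the same way. A site reading [11] with [10] would not go wrong. This stands as far as intent goes, and it is why the point is minor. It does not make the wording correct.

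On the SAP, Section 6.17 defines important deviations as violations of the protocol, and the table only paraphrases the criteria. Item [10] has no programmed check. A misflag needs a patient who stopped in the window, an elimination procedure, and a monitor who applies the SAP text over the protocol. The SAP revision history says the table follows a Trial Issue Management Plan, which is not among the documents, so what monitors were told is unknown. Section 6.17 also does not say which violations define the subset for its additional analyses. All of this stands: the consequence is possible but not demonstrated.

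Two smaller objections concern detail. A stop exactly 28 days before could count as within 4 weeks, since the strict inequality comes from the SAP programming note. That moves one boundary day and neither error. Changing an exclusion criterion also requires a protocol amendment, so the cost is more than one word of typing. That is right.

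**Conclusion.** Both errors are present in the current text. Protocol [11], read literally, excludes continuing leflunomide users whom [10] admits. SAP Table RHCF.6.9 [10] departs from protocol [10] and [11], and from the SAP's own [11], for stops at 4 to 12 weeks with elimination, a span of 56 days.

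The severity is minor. The ITT population keeps all randomized patients regardless of violation flags, so the primary and major secondary analyses, power and alpha do not change. The documents give no number of leflunomide users or stoppers, so no rate or patient count can be given. The result assumes that a patient still taking leflunomide has not had an elimination procedure, and it takes 4 and 12 weeks as 28 and 84 days. It does not depend on whether the elimination condition also applies to the first limb of [11], because both errors concern only current users and stops at 4 to 12 weeks.

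**What to change.** 1. In the second limb of protocol exclusion [11], replace *received* with *discontinued* and leave the rest of the sentence unchanged. The outcome then changes only for current users, who remain governed by [10].
2. In SAP Table RHCF.6.9, delete *leflunomide* from the discontinuation clause of item [10]. Item [11] then handles leflunomide stops alone, as in the protocol. Its 4-to-12-week window continues to rely on the monitor's list.

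The edits are one word changed and one word deleted, plus the usual amendment step for the protocol and a revision of the SAP. No patients, visits or procedures are added.

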6.3. Lifestyle Restrictions

Patients should be instructed to inform the blood bank of their participation in this study and consult with the investigator before donating blood or blood products during participation in the study.

6.4. Screen Failures

Individuals who do not meet the criteria for participation in this study (screen failure) may be rescreened under the following circumstances: patients who test positive for latent TB at screening may be rescreened following appropriate treatment as described in Section 9.4.4.2. Additionally, patients who do not qualify at screening under Exclusion Criterion [37] may be rescreened once, 4 or more weeks after documented resolution of symptoms. When rescreening is performed, the individual must sign a new ICF and will be assigned a new study identification number.

7. Treatments

7.1. Treatments Administered

This study involves a comparison of ixekizumab with adalimumab. Table RHCF.7.1 shows the treatment regimens.

Table RHCF.7.1. Treatment Regimens

Name of Drug	Starting Dose	Dosage	Frequency	Route of Administration
Ixekizumab	160 mg for all patients	80 mg	Q2W from Week 2 to Week 12 and Q4W thereafter for patients with moderate-to- severe plaque Ps	SC injection
			Q4W starting at Week 4 for patients not meeting criteria for moderate-to-severe plaque Ps	
Adalimumab	80 mg for patients with moderate-to-severe plaque Ps	40 mg	Q2W starting at Week 1 for patients with moderate-to-severe plaque Ps	SC injection
	40 mg for patients not meeting criteria for moderate-to-severe plaque Ps	.v mg	Q2W starting at Week 2 for patients not meeting criteria for moderate-to-severe plaque Ps	Se injection

Abbreviations: Ps = psoriasis; Q2W = every 2 weeks; Q4W = every 4 weeks; SC = subcutaneous.

The investigator or his/her designee is responsible for the following:

- explaining the correct use of the investigational agent(s) to the patient/site personnel
- verifying that instructions are followed properly
- maintaining accurate records of investigational product dispensing and collection
- at the end of the study returning all unused medication to Lilly, or its designee, unless the sponsor and sites have agreed all unused medication is to be destroyed by the site, as allowed by local law

7.1.1. Administration of Investigational Product

Injections will be administered subcutaneously by the patient or caregiver after training by the clinical staff.

Training: At randomization (Visit 2), patients randomized to ixekizumab and patients with moderate-to-severe plaque Ps symptoms randomized to adalimumab will receive 2 injections. For training purposes, the proper procedures for administration of the initial injection will be performed by clinical staff. The second injection of study drug will be administered by the patient or caregiver under site personnel supervision. Thereafter, study drug should be administered by the patient or caregiver. If additional training is necessary, an injection may be administered by the patient or caregiver under the supervision of clinical staff.

Administration: If the patient is unable to administer the injection, a caregiver who will also be trained under supervision of site staff may administer the study drug. All subsequent injections will be administered by the patient or caregiver and should be administered unsupervised by the clinical staff (see Section 2). It is recommended that for these subsequent injections, the patient/caregiver administer the study drug outside the trial site, preferably at the patient's home. If the patient or caregiver is not able to administer the second injection of the starting dose or any dose throughout the study, study site personnel may administer that injection.

Refer to the appropriate directions for use provided by the sponsor for the study drug.

Study Drug Administration Logs will be dispensed to each patient as needed for recording pertinent data about each injection; details of the use of these logs are provided in Section 7.2.1.

Observation: Patients should remain under observation for at least 1 hour after dosing at randomization (Visit 2) to allow for observation for any AEs and collection of postinjection sitting BP and pulse measurements approximately 1 hour after administration of study drug (see Section 2).

7.1.2. Packaging and Labeling

Clinical trial materials will be labeled according to the country's regulatory requirements. All investigational products will be stored, inventoried, reconciled, and destroyed according to applicable regulations.

Ixekizumab will be supplied as an injectable solution in 1-mL, single-dose, prefilled, disposable manual syringes with study-specific labels. Each syringe of ixekizumab is designed to deliver ixekizumab 80 mg.

Adalimumab 40 mg will be supplied as single-dose, prefilled, disposable manual syringes with study-specific labels.

Syringes will be supplied in cartons with the appropriate quantity of syringes specific to the planned dispensing schedule of the investigational product.

7.2. Method of Treatment Assignment

Patients who meet all Visit 1 and Visit 2 eligibility criteria for enrollment will be randomized at Visit 2 (Week 0) in a 1:1 ratio to open-label treatment with ixekizumab or adalimumab at Week 0 (Visit 2). Assignment to treatment groups will be determined by a computer-generated random sequence using an interactive web-response system (IWRS). The IWRS will be used to assign investigational product to each patient. Site personnel will confirm that they have located the correct investigational product by entering a confirmation number found on the investigational product into the IWRS. The randomization will be stratified by concomitant csDMARD use at baseline (Yes vs No) and moderate-to-severe plaque psoriasis involvement (Yes vs No).

7.2.1. Selection and Timing of Doses

Patients taking ixekizumab or adalimumab will receive the open-label study drug beginning on the day of Visit 2 (Week 0).

Study drug should be administered on the same day of the week, at approximately the same time each day, as much as possible. If an injection is missed, the missed dose should be administered as soon as possible. Injection(s) for missed dose(s) should not be given within 5 days of the next scheduled dose; injections should be ≥ 5 days apart. Dates of subsequent study visits should not be modified according to this delay.

A paper Study Drug Administration Log will be completed by randomized patients for each injection throughout study participation. The data from the Study Drug Administration Log must be transcribed into the electronic case report form (eCRF) by site personnel.

Patients will be instructed to contact their study site in the event of an injection problem. In addition, site personnel review all Study Drug Administration Logs at each visit to identify any product complaints, and they will complete a product complaint form for each operation failure reported on a Study Drug Administration Log (see Section 9.2.2 for additional instructions regarding complaint handling).

7.3. Blinding

This is an open-label study where treatment allocation is revealed after randomization. Specifically:

- A blinded assessor will complete the following assessments:
 - o TJC/SJC
 - o Psoriasis Area and Severity Index (PASI)
 - Percentage of BSA
 - o Enthesitis
 - o LDI-B
 - NAPSI Fingernails
 - o sPGA

The blinded rater must not know the patient's treatment allocation and is not allowed to be otherwise involved in the study procedures.

The patients will be clearly instructed not to communicate with the blinded assessor except for communication required to conduct the blinded data assessment. During each procedure conducted by a blinded assessor, a third person from the study site (eg, a nurse) will be present to observe and document that blinding of the assessor is maintained. If a blinded assessor is unintentionally unblinded, he/she must be replaced as an assessor.

The availability of a blinded assessor is a prerequisite for study site selection.

